5.4.4 Multiplicity

Multiplicity adjustment will not apply to the primary and secondary outcome analyses.

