Sample size was calculated estimating the efficacy of the different experimental drug or combinations for each of the STH of interest (57,58), and gathering the individual samples sizes for the study. The sample size was calculated for pairwise comparisons of the expected Cure Rates for three study groups with an overall significance level of 5% adjusted for multiple tests by Bonferroni's correction, 80% power and inflated for 10% lost-to-follow-up.

The estimated total number of participants for the adaptive design is 1223 (*T. trichiura* 625, *S. stercoralis* 286 and hookworm 312). This sample size is powered to be able to measure efficacy for all three species in the phase III component. The sample size for the phase II component is 20% of the total participants for *T. trichiura* (126 participants). The remaining 80% of the *T. trichiura* participants will be randomised in the phase III component. Table 2 details the stratification of the participants per species with a 10% lost-to-follow-up.

The total number of participants to be included in this clinical trial is 1223 (126 in phase II and 1097 in phase III). Following randomisation, 251 participants will be allocated to the ALB treatment arm, 427 will be allocated to the FDC treatment arm and 419 in the FDCx3 treatment arm. Table 2 details the stratification of the participants per species with a 10% lost-to-follow-up.

The 10% lost-to-follow-up inflated sample sizes of the ALB-group for *T. trichiura*, *S. stercoralis* and hookworm are 129, 47 and 101 respectively, and the corresponding sample sizes of the individual experimental treatment groups are 248, 120, and 101 for FDC-group and 248, 119 and 110 for FDCx3-group. The corresponding powers of each of the tests are 91%, 100% and 80% to compare the CRs of *T. trichiura* in ALB *vs* FDC, ALB *vs* FDCx3 and FDC *vs* FDCx3 respectively; 95%, 100% and 80% to compare the

Version 4.0 21st January 2022

ALIVE Study

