3.5 Determination of sample size

Sample size was calculated based on available data from peer-review publications complemented with reasonable estimates of efficacy for those experimental groups that have not been previously tested. For these calculations, the efficacy of the control arm (Albendazole 400mg in a single dose), was obtained for *T. trichiura* and hookworms from a systematic review and meta-analysis where

temporary trends in efficacy (with the corresponding confidence intervals) were incorporated (Table 3)[4]. For the efficacy of the control arm against *S. stercoralis*, an alternative source was used [5], since the systematic review by *Moser et al* did not include this species; for that reason, a clinical trial that included an arm of Albendazole 400mg for 3 consecutive days was used, assuming a "best case scenario" for the efficacy of the control group; this estimated efficacy is also in the range of a systematic review assessing the efficacy of Albendazole at various (but not single) doses[5]. For the FDC at single dose, the calculations were based on the estimated efficacies (and their corresponding confidence intervals) in a systematic review that calculated the Relative Risks of cure of diverse drug regimens against Albendazole 400mg single dose (Table 3)[6,7]. For. *S. stercoralis*, the estimated efficacy of FDC was calculated based on a recent clinical trial using lvermectin single and multiple-dose regimens [8]. Finally, for the FDC in 3-dose regimens, considering its use in public health, deployment logistics in MDA campaigns and expected impact of the FDC, we estimated that an improvement of at least 15 percentage points would be the minimum improvement in efficacy to be demonstrated in order to make the FDCx3 regimen worth considering.

Sample size was calculated estimating the efficacy of the different experimental drug or combinations for each of the STH of interest [9,10], and gathering the individual samples sizes for the study. The sample size was calculated for pairwise comparisons of the expected Cure Rates for three study groups with an overall significance level of 5% adjusted for multiple tests by Bonferroni's correction, 80% power and inflated for 10% lost-to-follow-up.

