3.6 Study stopping guidance

The following stopping rules will apply at relevant key instances in the ALIVE study:

- **ISGIODAI** Barcelona Institute for Global Health
 - The occurrence of ≥1 serious adverse reaction (where causality is at least possible) or SUSAR in any of the weight groups in the Phase II will result in suspension of dose escalation in the FDC arm pending review by the DSMB (keeping in mind the sequential recruitment strategy in phase II).
 - 2. The occurrence of ≥2 serious adverse reactions or SUSARs at the end of phase II will result in suspension of progress to phase III pending review by the DSMB.

Overall the occurrence of serious adverse reactions or suspected unexpected serious adverse reactions in 2% of the study populations at interim analysis (50% recruitment) will result in suspension of further dosing of the Investigational Product pending review by the DSMB. This is equivalent to 12 safety events which meet these criteria in 612 participants recruited at the point of the interim analysis.

Table 3. Sample size and power calculation according to the expected efficacy (Cure Rate) of the different treatment arms

Comparison Trichuris trichiura	Target Power	Actual Power	Sample Size	Expected Cure Rate	Overall Alpha	Bonferroni adjusted Alpha
ALB vs IVM-ALB vs (IVM-ALB)x3 IVM-ALB vs (IVM-ALB)x3	80% 80% 80%	91% 100% 80%	116 223 223	23.7% 43.7% 59%	0.05 0.05 0.05	0.0167 0.0167 0.0167
Strongyloides stercoralis ALB vs IVM-ALB vs (IVM-ALB)x3	80% 80%	95% 100%	42 108 107	45% 79% 94%	0.05 0.05	0.0167 0.0167
IVM-ALB vs (IVM-ALB)x3 Hookworm ALB vs IVM-ALB vs (IVM-ALB)x3 IVM-ALB vs (IVM-ALB)x3	80% 80% 80% 80%	80% 82% 80%	91 91 99	79.5% 79.5% 95%	0.05 0.05 0.05 0.05	0.0167 0.0167 0.0167 0.0167

	Pł	nase II		PHASE III		PHASE II/III
		N total			N tota	al
		Phase			Phase	
Group	N	II ¹	Ν		III ¹	N total
Trichuris trichiura						
ALB	23	26	93		103	129
FDCx1	45	50	178		198	248
FDCx3	45	50	178		198	248
Total	113	126	449		499	625
Strongyloides.						
stercoralis						
ALB			42		47	47
FDCx1			108		120	120
FDCx3			107		119	119
Total		0	257		286	286
Hookworm						
ALB			91		101	101
FDCx1			91		101	101
FDCx3			99		110	110
Total		0	281		312	312
TOTAL		126			1097	1223

Table 4. Final sample size calculation taking into account 10% lost-to-follow-up

¹Calculated by inflating the sample size using considering 10% lost-to-follow-up

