5.3 Efficacy analysis

5.3.1 Hypothesis

The main hypothesis is that FDC (either at single or 3-day regimens) will be more effective against STH than the current strategy (single dose ALB alone).

Specific hypotheses:

- Primary Efficacy Endpoint: Higher estimated CR for *T. trichiura* 21 days after treatment, using microscopy in participants allocated to arms 2 and 3 than to arm 1.
- Secondary Efficacy Endpoint(s):
 - Higher estimated CR for hookworm and *S. stercoralis* 21 days after treatment using microscopy in participants allocated to arms 2 and 3 than to arm 1.
 - Higher estimated ERR for *T. trichiura* 21 days after treatment using microscopy in participants allocated to arms 2 and 3 than to arm 1.
 - Higher estimated CR for hookworm, *T. trichiura* and *S. stercoralis* 21 days after treatment, using qPCR in participants allocated to arms 2 and 3 than to arm 1.

5.4 **Primary efficacy outcomes analysis**

The primary efficacy endpoint for the efficacy phase III trial is the cure rates for *T. trichiura* 21 days after treatment using microscopy. The analysis will be conducted on the ITT population and in the sensitivity population (per protocol). The analysis will include both Phase II and Phase III participants. The Cochran–Mantel–Haenszel (CMH) test, controlling the effect of site if that is appropriate (sufficient participants), will be used to compare the cure rates for the 3 treatment groups. A participant is considered cured if the baseline egg count or larval count is not 0, and the post-treatment egg count or larval count is 0. Similarly, a participant is considered to have treatment failure if the baseline egg or larval count is not 0.

A total of 2 stool samples (1 pre-treatment and 1 post-treatment) will be obtained from each participant. The primary efficacy analysis will be based on ITT population. Efficacy for each type of infection will be analysed separately. A participant with multiple infections will be included in the analysis of each target species that the participant is infected with.

Stool sample collected pre-treatment will be used for the baseline information, and stool sample collected post-treatment will be used for the post-treatment information in the statistical analysis.

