5.7 Interim analyses

Two interim analyses are planned: 1) after the end of the phase II component for decision making to move to the phase III component; 2) after 50% of the study participants are enrolled. Regular evaluation of the safety data every 3 months will be performed by the DSMB. The study is designed as a superiority trial, so all tests will be two-sided and an overall significance level will be 0.05 In the interim efficacy analysis, the expense function alpha with the O'Brien-Fleming approach will be used to determine the type I error rate for each interim and final analysis.

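### The SAP drops multiplicity adjustment for the primary analysis, although T. trichiura is sized on three pairwise tests at 0.0167; the level of those tests is left open

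*SAP*

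**What the plan says.** **Sizing.** SAP 3.5 bases the sample size on pairwise comparisons of three groups at an "overall significance level of 5% adjusted for multiple tests by Bonferroni's correction, 80% power and inflated for 10% lost-to-follow-up". Protocol 9.2 says the same: "pairwise comparisons of the expected Cure Rates for three study groups with an overall significance level of 5% adjusted for multiple tests". SAP Table 3 and Protocol 9.2 Table 1 list three T. trichiura comparisons, each with 0.0167 under "Bonferroni adjusted Alpha". For the three-day regimen, SAP 3.5 adds: "we estimated that an improvement of at least 15 percentage points would be the minimum improvement in efficacy to be demonstrated".

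**Analysis.** SAP 5.4 gives one primary test, a CMH test that, "controlling the effect of site if that is appropriate (sufficient participants), will be used to compare the cure rates for the 3 treatment groups". Protocol 9.5.2 is the same in substance. Neither names a pairwise test, a level for it, an order or a gate.

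**Error rate.** SAP 5.4.4: "Multiplicity adjustment will not apply to the primary and secondary outcome analyses". SAP 5.7: "so all tests will be two-sided and an overall significance level will be 0.05". On repeated looks, that section adds: "the expense function alpha with the O'Brien-Fleming approach will be used to determine the type I error rate for each interim and final analysis". Protocol 9.5.1 sets 0.05 for every significance statement.

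**Hypotheses.** The main hypothesis in SAP 5.3.1 is met by the single-dose or the three-day regimen. The specific primary hypothesis sets arms 2 and 3 against arm 1. FDC vs FDCx3 is not listed there.

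**The concern.** The sizing text promises an overall 5% shared over three pairwise tests, and the analysis text says nothing is to be shared. The one named test does not bridge the gap: a significant three-group result does not tell the reader whether one dose beats ALB, whether three doses do, or whether three beat one. Those are the conclusions the trial is meant to support, and each needs a pairwise test.

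O'Brien-Fleming spending controls error over repeated looks at one comparison. It does nothing for several comparisons among arms.

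With the level unwritten, two analysts following the same SAP could disagree on a pairwise p-value of 0.03: significant at 0.05, not at 0.0167. If the level is picked after the results are known, the overall 5% is lost on the primary endpoint.

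**Working it through.** **Inputs.** Evaluable n 116/223/223 (ALB/FDC/FDCx3), inflated to 129/248/248; cure rates 23.7%, 43.7%, 59%; stated powers 91%, 100%, 80% (SAP 3.5 and Tables 3 and 4; Protocol 9.2). Two-sided tests (SAP 5.7). Missing outcomes counted as failures (SAP 4.1, 5.1.5). Loss 10%.

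**1. Reproduce the plan's figures.** 0.05/3 = 0.0167, so z = 2.394. Pooled two-proportion power is Φ[(d − z·s0)/s1], where s0 is the pooled standard error and s1 the unpooled one.
- ALB vs FDC: d = 0.200, s0 = 0.0552, s1 = 0.0516, argument 1.314, power 90.6% (stated 91%).
- ALB vs FDCx3: d = 0.353, power 100.0% (stated 100%).
- FDC vs FDCx3: d = 0.153, s0 = 0.0473, s1 = 0.0468, argument 0.848, power 80.2% (stated 80%).
- Required n for FDC vs FDCx3 at 80% power: 223 per arm, as stated. Inflation: 116/0.9 → 129 and 223/0.9 → 248, as stated.

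**2. The same at unadjusted 0.05.** The powers would be 96.2%, 100.0% and 90.1%, and FDC vs FDCx3 would need 167 per arm. The stated 223 therefore depends on the Bonferroni level.

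**3. Family-wise error, one look.** The two comparisons with ALB share a control, so their correlation is 223/(116 + 223) = 0.658. The chance that at least one exceeds 1.96 when all arms are equal is about 8.5%, which simulation confirms (8.5–8.6%). Independence would give 1 − 0.95² = 9.75%.

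**4. Family-wise error with the spending rule.** Assumptions: one efficacy look at 50% of the T. trichiura information plus the final analysis; nominal levels 0.00305 and 0.0490, so one third is 0.0010 and 0.0163; 400,000 simulated trials per scenario; common cure rate 0.237, 0.437 or 0.59; no site effect.

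| Rule | 116/223/223 | 187/187/188 |
|---|---|---|
| Two pairs vs ALB, unadjusted | 8.6–8.7% | 9.1–9.3% |
| All three pairs, unadjusted | 12.2–12.4% | 12.1–12.3% |
| All three pairs, one third of the level | 4.3–4.4% | 4.4–4.5% |
| Pairs only after a significant three-group test | 5.0–5.1% | 5.0–5.1% |

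Moving the look to 30% or 70% information (rate 0.237) leaves these unchanged: 8.6%, 12.2%, 4.3–4.4%, 5.0%. A different O'Brien-Fleming-type form (0.0056 and 0.0478) gives 8.7%, 12.2%, 4.4% and 5.0%. With only one pair truly equal, the gated rule still gives 5.0–5.1%.

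**5. Power under the two valid rules, over two looks.** In the ITT rows the cure rates are multiplied by 0.9, because the 10% lost count as failures.

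| Comparison | One third of level | Gated |
|---|---|---|
| FDC vs FDCx3, evaluable 223/223 | 79.6% | 90.3% |
| ALB vs FDC, ITT 129/248 | 88.9% | 95.2% |
| ALB vs FDCx3, ITT 129/248 | 100.0% | 100.0% |
| FDC vs FDCx3, ITT 248/248 | 75.9% | 87.6% |
| FDC vs FDCx3, ITT at 1:1:1 (208/208/209) | 67.7% | 80.7% |

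**The case against.** The best defence is that there is one primary efficacy endpoint and one named three-group test, which holds 5% by itself; 5.4.4 may then mean only that nothing is adjusted across outcomes. Further, if the specific hypothesis requires both regimens to beat ALB, no adjustment is needed (error about 1.4–1.5% with all arms equal). The overall 0.05 in SAP 5.7 may refer only to looks. The 12% figure depends on FDC vs FDCx3, which is in neither the primary objective nor the listed hypotheses. Table 3 also applies 0.0167 to S. stercoralis and hookworm, so sizing should not bind for one species alone.

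Part of this stands. The inflation is conditional on how the pairs are tested. For the listed hypotheses the figure is about 8.6%. The overall 5% across arms rests mainly on the sizing text. The fall in FDC vs FDCx3 power from 80% to 76% comes from counting losses as failures, not from the multiplicity rule.

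The rest does not rescue the plan. The both-must-win reading conflicts with a main hypothesis that either regimen can satisfy. The three-group test cannot support a claim about one regimen. A gate would be valid, but neither document states one, and Protocol 9.5.1 read as the pairwise level contradicts the 0.0167 directly. FDC vs FDCx3 sets the size of the experimental arms, and its gain is described as one to be demonstrated, so it needs a stated status.

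**Conclusion.** The concern holds. The plan's powers and n reproduce at 0.0167, while SAP 5.4.4 removes the adjustment and leaves the pairwise level unstated. Ungated pairs at the unadjusted level, which 5.4.4 permits, give about 8.6% for the two comparisons with ALB (9.1–9.3% at 1:1:1) and about 12% for all three, against the stated 5%. One third of the level, or a three-group gate, restores about 4.3% or 5.0%.

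The error figures assume equal cure rates in all arms, one efficacy look plus the final, and no site effect; they barely move with the timing of the look or the spending form. The power figures are provisional, because Protocol 4.1 (1:1:1) conflicts with Protocol 6.1.2 and SAP 3.3 (unequal, 0.2/0.4/0.4).

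**What to change.** Put the rule in the SAP before the 50% efficacy interim, since it sets the level used there, and in any case before database lock.

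- **SAP 5.4 and 5.4.4:** for T. trichiura cure, test ALB vs FDC, ALB vs FDCx3 and FDC vs FDCx3 each by a two-sided CMH test with the site handling already planned, at one third of the O'Brien-Fleming level for that analysis. This matches the sizing.
- **Acceptable alternative:** test the pairs at the full O'Brien-Fleming level, but only if the three-group CMH test is significant at that level at the same analysis.
- **SAP 5.3.1:** list FDC vs FDCx3.
- **SAP 5.4.4:** limit the no-adjustment sentence to secondary outcomes and say their p-values carry no overall error control. For S. stercoralis and hookworm, say that the 0.0167 in Table 3 was a planning level only.
- **Protocol 9.5.1:** align the 0.05 statement at the next amendment, with the IRB/EC approval that Protocol 10.1 requires.

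The cost is wording, with no added participants or data. The choice between the rules matters for FDC vs FDCx3: under ITT with 10% loss, one third of the level gives about 76%, below the 80% target, and the gate about 88%. At 1:1:1 these become about 68% and 81%, so the allocation ratio must be reconciled before the power is restated.

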5.5 Safety analysis

Safety analysis in the phase II corresponds to the primary outcome/endpoint, i.e, the frequency, type, severity and relationship to study drug for all adverse events and severe adverse events. For the safety analysis in phase III, the safety population will be used for the analysis and participants will be considered by arm and by both FDC arms pooled (overall) and by number of doses of FDC received to explore dose-responses.

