**ALIVE Study** 

21st January 2022 In children, doses of 400 µg/kg have been tested in clinical trials to evaluate treatment for head lice. This dosage was well tolerated, although 1.8% of participants (7 of 398) discontinued treatment because of adverse events (similar to control group receiving 0.5% malathion lotion) (29). Dose finding studies performed in Ivory Coast for the treatment of infections with T. trichiura in children have also demonstrated that regimens of 200, 400 and 600µg/Kg had adverse event rates similar to placebo (25) in terms of type, frequency and severity. The current use of IVM is restricted to populations ≥15 kg. This limitation, albeit not based on evidence demonstrating either lack of efficacy or added toxicity represents an obstacle in two different aspects of public health: 1. Excludes significant groups of the at-risk population from the benefits of IVM; 2. By lowering the absolute coverage of the interventions, it decreases the likelihood of transmission interruption and disease elimination.

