**ALIVE Study** 

21st January 2022 be allowed more than one repeated dose. In case that a participant vomits following re-dosing during enrolment visit, the subject will be withdrawn from the trial and standard treatment will be offered according to national guidelines. Light meal is considered as a soft breakfast with a contribution of 15 g of fat. It might be defined as 250 cc of milk with tea or coffee, 1 tablespoon full sugar (25 g) and 25 g of fat biscuits. The expected nutrient contribution is approximately 312.8 calories: 38.43 g of carbohydrates,

4.81 g of proteins and 15.5 grams of fats.

Detailed instructions for dose administration, and storage conditions will be provided to each study site.

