# 7.2 PARTICIPANT WITHDRAWAL FROM THE STUDY

Subjects who have been enrolled and, for whatever reason, discontinue the trial prematurely after randomization are classified as withdrawals. Subjects may withdraw from the trial at any time, either on their own request (withdrawal of consent/assent) or at the discretion of the investigator.

Participants are free to withdraw from participating in the study at any time.

In addition, an investigator may prematurely discontinue a participant from the study for the following reasons:

- Pregnancy
- Significant study intervention non-compliance
- If any clinical adverse event (AE), laboratory abnormality, or other medical condition or situation
  occurs such that continued participation in the study would not be in the best interest of the
  participant
- If the participant meets an exclusion criterion (either newly developed or not previously recognized) that precludes further study participation (Screening error resulting in incorrect enrolment)
- Participant unable to receive study drug as per protocol.
- Other conditions that upon judgement of the Investigator or the DSMB, could hamper the safety of an individual and/or the validity of the study.

The reason for participant withdrawal from the study must be recorded in the subject's medical records and CRF. Participants who provide informed consent and assent forms and are randomized but do not receive the study intervention may be replaced. Participants who sign the informed consent form, and

Version 4.0

ALIVE Study 21st January 2022

are randomized and receive the study intervention, and subsequently withdraw consent, or are discontinued from the study, will not be replaced.

Participants who discontinue from the study will be assessed for adverse events.

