2.2.2 Secondary outcomes

Treatment efficacy: Anti-helminthic efficacy, measured through egg reduction rate (ERR), will be determined by analysing a stool sample taken 21(+/-7) days after completing treatment with Kato Katz[2]. Egg reduction rate (ERR) will be calculated by using geometric means, calculated for hookworms, *T. trichiura* and *A. lumbricoides*. In addition, Anti-helminthic efficacy, measured by cure

¹⁸ Age, Date of Birth, Sex, Participant ID, Guardian relationship, age and contact details

²⁰ Vital signs should Include heart rate, respiration rate, body temperature and blood pressure.

¹⁴ Informed consent will be obtained from parents or guardians of all participants <18years. Informed consent/assent can be performed up to 3 months prior to screening visit as part of the pre-screening activities OR during screening visit

 $^{^{\}rm 15}$ Assent to participate in the trial will be obtained from participants 12-17 years old.

¹⁶ A stool collection kit will be provided to participants for the collection of stool samples after providing assent and consent. The stool should be collected <24 h before examination for eligibility check. An aliquot of the collected stool sample will be stored for QC by PCR to confirm microscopic results from Kato-Katz and Baermann test if microscopy positive at screening and for all follow-up stool samples. All samples will be tested at site. Should technical issues arise or in case of discrepancy in results, an aliquot of the stool sample will be tested abroad for QC purposes.

¹⁷ Lab tests will be performed on a fresh stool sample collected <24 hours before examination.

¹⁹ Physical exam should include clinical diagnosis of scabies (rush/lesions on skin) before and after treatment. During unscheduled visits Physical exam will be performed only if necessary.

²¹ A urine test kit will be provided in order to collect urine sample from all participants which will be examined by haematuria strip test as a proxy *for* Schistosoma eggs and to confirm negative pregnancy test for female participants \geq 12 years old or post-menarche.

²² Serum HIV test will be offered only to eligible participants at the Manhiça site in Mozambique because of high HIV prevalence.

²³ Treatment Day 0. For all participants in Arms 1, 2 and 3. Treatment dose will be given under direct supervision.

²⁴ Treatment Day 1. Only for participants in treatment Arm 3. Close observation for 3 hours post-treatment for safety evaluations.

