5.2.6 Study drug administration

For the single dose treatment arms, the number and percentage of participants who receive study drug will be summarized. For the repeat dose treatment arm, the number and percentage of participants who receive 1, 2, or 3 doses of study drug will be provided.

Study drug administration will be presented in a data listing.

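### The phase III safety dose-response view groups children by FDC doses received, which adverse events can change, so it is biased towards showing no dose effect and can reverse

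*SAP*

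**What the plan says.** For phase III safety, SAP 5.5 says that "participants will be considered by arm and by both FDC arms pooled (overall"), and then adds a third view, "by number of doses of FDC received to explore dose-responses". Protocol 9.5.4 plans the same three views.

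The SAP expects the third view to have several levels within the 3-day arm. Section 5.2.6 states: "For the repeat dose treatment arm, the number and percentage of participants who receive 1, 2, or 3 doses of study drug will be provided".

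The documents also show how an AE can shorten dosing:

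- Protocol 7.2 lets the investigator discontinue a child, one listed ground beginning "If any clinical adverse event (AE), laboratory abnormality, or other medical condition or situation".
- Protocol 6.1.2 says of a child who vomits again after re-dosing at enrolment that "the subject will be withdrawn from the trial".
- SAP 5.5.1 plans listings of treatment-emergent AEs that lead to withdrawal or interruption of study drug.

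Children who stop treatment are not lost to the safety data. Protocol 7.1 has them complete the remaining visits, and Protocol 7.2 has those who leave the study assessed for AEs. Neither document links an AE to the doses given before its onset, or separates a planned single dose from a 3-day course cut short.

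**The concern.** The number of doses received is fixed after randomisation and can be changed by the outcome under study. If a 3-day-arm child has an AE after dose 1 and stops, the grouping places that child, with the event, beside the whole single-dose arm. A stop after dose 2 creates a 2-dose group made up only of children who did not complete treatment. In both cases the 3-dose group loses a child with an event. AE-driven stopping therefore lowers the 3-dose rate, and stops after dose 1 also raise the 1-dose rate.

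The trial is meant to show whether repeated high-dose ivermectin is acceptable in children. A table labelled as dose-response that shows similar or lower AE rates with more doses could be read as reassurance when it only reflects who stopped.

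**Working it through.** **Inputs.** The plan states no figure for this analysis, so there is none to reproduce. Two document figures are used.

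- Stopping share: Protocol 2.2 reports that "1.8% of participants (7 of 398) discontinued treatment because of adverse events" in a trial of 400 µg/kg for head lice; 7/398 = 1.76%. This is another indication and only a guide.
- Arm sizes: Protocol Table 2 sums for phase III to FDC 198 + 120 + 101 = 419 and FDCx3 198 + 119 + 110 = 427. The text of Protocol 9.2 gives 427 and 419, apparently swapped. Swapping them changes the results by 0.2 points or less.

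All AE risks, and stopping shares other than 1.8%, are assumptions.

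**Formulas.** Let q1 and q3 be the true AE risks in the FDC and FDCx3 arms, n1 and n3 their sizes, and s the share of the FDCx3 arm that stops after dose 1 because of an AE. Then

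- 1-dose rate = (q1·n1 + s·n3)/(n1 + s·n3)
- 3-dose rate = (q3 − s)/(1 − s)

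With equal arms the size cancels: the 1-dose rate is (q1 + s)/(1 + s), and the gap is zero at s = (q3 − q1)/(2 − q1 − q3).

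**Case A: 10% against 15%, equal arms, all stops after dose 1.** True gap +5.0 points.

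| s | 1-dose | 3-dose | Gap (points) |
|---|---|---|---|
| 1.8% | 0.118/1.018 = 11.6% | 0.132/0.982 = 13.4% | +1.9 |
| 3% | 0.130/1.030 = 12.6% | 0.120/0.970 = 12.4% | −0.3 |
| 5% | 0.150/1.050 = 14.3% | 0.100/0.950 = 10.5% | −3.8 |

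The gap is zero at s = 0.05/1.75 = 2.9%.

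**Case B: as A, but half the stops come after dose 2.** The 1-dose rate becomes (q1 + s/2)/(1 + s/2) and the 3-dose rate is unchanged. At 1.8% the rates are 10.8% and 13.4% (+2.6). At 3% they are 11.3% and 12.4% (+1.0). At 5% they are 12.2% and 10.5%, still reversed. The 2-dose group shows an AE rate of 100%.

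**Case C: equal 10% risk at each dose.** The three-dose risk is 1 − 0.9³ = 27.1%, a true gap of 17.1 points. With all stops after dose 1, the gap is +14.2 at 1.8%, +12.2 at 3% and +9.0 at 5%. Zero would need s = 0.171/1.629 = 10.5%.

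**Case D: rare severe AEs, 1% against 3%, arms of 419 and 427.** Expected events are 4.19 and 12.81. True gap +2.0 points.

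- Four stoppers: (4.19 + 4)/423 = 1.9% against (12.81 − 4)/423 = 2.1%, so the gap is almost gone.
- Five stoppers: 9.19/424 = 2.2% against 7.81/422 = 1.9%, so it is reversed.

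Grouping by the arm started keeps each child, and any AE, in the randomised group in all four cases.

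**The case against.** The strongest reply is that little depends on this table. The same sentence in SAP 5.5 plans safety by arm, and FDC against FDCx3 is the randomised contrast of one dose with three. SAP 5.5.1 regresses drug-related events on regimen, not on doses received. The view is worded as exploratory and limited to phase III. The counts of children who received 1, 2 or 3 doses and the listings of events leading to withdrawal would expose the stoppers, and a 2-dose group of non-completers would be conspicuous. All of this stands. It limits the weight of the point but does not remove the bias from the table.

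The size is also open to challenge. Cases B and C show that it depends on when children stop and on the true risks. The 1.8% comes from another indication, where discontinuation was similar to control, and 3% and 5% have no source. Some missed doses will be due to school absence rather than intolerance. This too stands.

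Three stronger readings are tempting but not supported:

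- A reader might infer that this is the only planned look at safety by dose. It is not, because of the by-arm summaries and the regression.
- A reader might infer that a single-dose child re-dosed after vomiting moves to a 2-dose group. Neither document says so, and SAP 5.2.6 applies the 1, 2 or 3 count only to the repeat-dose arm. It is a gap to close.
- A reader might infer that the arms are observed on very different schedules. AE monitoring is common to all arms on Days 0, 1, 2, 3, 7 and 21. What differs is the watch after the Day 1 and Day 2 doses: "Only for participants in treatment Arm 3. Close observation for 3 hours post-treatment for safety evaluations". That affects the by-arm view as well.

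**Conclusion.** The point holds for the view by doses received. Followed as written, it moves children who stop because of an AE out of the 3-dose group, so the bias runs towards no dose effect and can go past zero. For common AEs the size ranges from modest shrinkage (Case C) to loss of the gap at about 3% stopping and reversal at 5% (Case A). For rare severe AEs, four or five children are enough under the assumed risks. These results rest on assumed AE risks and stopping shares and, except in Case B, on all AE stops coming after dose 1. If no child stops because of an AE, this bias does not arise. The by-arm safety comparison is not subject to this reallocation. This is a worthwhile, inexpensive improvement to an exploratory analysis, not a threat to the trial's main safety conclusions.

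**What to change.** In SAP 5.5 and Protocol 9.5.4, name FDCx3 against FDC as the safety dose-response analysis, with children analysed by the arm started, whether or not later doses were taken. Optionally split it by AE onset: before the Day 1 dose, when the two FDC arms have had the same planned exposure, and after it. Show separately AEs whose onset day was imputed under SAP 5.1.5, because that rule can move an AE with a missing start day to the first-dose date and so into the early interval.

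If a table by doses received is kept, count only doses given before AE onset, with the children who reached that count as the denominator. State that, for this analysis, a re-dose after vomiting is not an additional dose level, and label the table descriptive.

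The cost is wording and a few more tables. AE onset date and time (Protocol 8.3.3.1) and study drug administration (SAP 5.2.6) are already recorded, and trial conduct does not change. One small downside is that the by-arm contrast is diluted when children stop early, which the planned counts of doses received will make visible.
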